8.3. Recording and Reporting of Serious Adverse Events and Unanticipated Problems

SAEs and UPIRSOs will be reported per governing IRB policy and procedure.

- UPIRSOs that are a result of study participation are reported to the IRB and the Medical Safety Officer within 24 hours. The report will include a description of the event, when and how it was reported, as well as any official chart records or documentation to corroborate the event or the reporting of the event. All adverse events will be graded as mild, moderate, or severe.
- SAEs will also be submitted to the IRB and the safety officer within 24 hours.
- SAEs that are still ongoing at the end of the study period will be followed up to determine the final outcome. Any SAE that occurs after the study period and is considered to be possibly related to the study treatment or study participation will be recorded and reported per Institutional policy and according to FDA requirements.

Any action resulting in a temporary or permanent suspension of this study (e.g. local site IRB actions) will be reported to the IND Sponsor.

Investigator reporting: notifying the IND sponsor

Any study-related UPIRSO, and any type of SAE, must be reported to IND Sponsor by telephone within 24 hours of the event. To report such events, a Serious Adverse Event (SAE) form must be completed by the investigator and faxed to IND sponsor within 24 hours. The investigator will keep a copy of this SAE form on file at the study site.

Report SAE/UPIRSOs by email or facsimile to:

[name] Associate Professor, Department of Medicine

0008_Protocol v2.5, 08-03-18, AMD.docx

OXY-SAR-001 Version: 2.5

> University of Texas Health Science Center at San Antonio Barshop Institute for Longevity and Aging Studies [name] [contact] (phone) – [contact] (fax) Email: [contact]

Within the following 48 hours, the investigator must provide further information on the SAE or the UPIRSO in the form of a written narrative. This should include a copy of the completed SAE form, and any other diagnostic information that will assist the understanding of the event.

Reporting Process: Notifying the UTHSCSA IRB

Adverse events not requiring immediate reporting may be tracked at each site on UTHSCSA Adverse Event Tracking Form (Track both UPIRSO and Events and Problems Not Requiring Prompt Reporting) and will be collected in REDCap. For SAE and UPIRSO, use UTHSCSA Prompt Reporting Form.

Sponsor reporting: Notifying the FDA

• Within 7 calendar days

Any study event that is:

- associated with the use of the study drug
- unexpected,
- fatal or life-threatening, and

Within 15 calendar days

Any study event that is:

- associated with the use of the study drug,
- unexpected, and
- serious, but not fatal or life-threatening -or-
- previous adverse event that was not initially deemed reportable but is later found to fit the criteria for reporting (reporting within 15 calendar days from when event was deemed reportable).

Any finding from tests in laboratory animals that:

 suggest a significant risk for human subjects including reports of mutagenicity, teratogenicity, or carcinogenicity.

Sponsor Reporting Process

Serious adverse events may be submitted on FDA Form 3500A or in a narrative format. The contact information for submitting IND safety reports is noted on the next page.

Food and Drug Administration Center for Drug Evaluation and Research Division of Metabolism and Endocrinology Products [name] [name] 20705-1266 [contact] [contact]

8.5. Unblinding Procedures

See Section 8.3 – For SAE or SAE-UPIRSO, the site investigator must report within 24 hours of the event to IND Sponsor who confers with Medical Safety Officer (Section 8.4) to assess the need for initiation of stopping rules or unblinding procedures. Responsibilities of each individual are bulleted below.

Medical Safety Officer

- Assess SAE or SAE-UPIRSO to determine if unblinding is required and, if yes, notify pharmacist to request subject's assignment
- Compare event data to intervention/assignment to determine if SAE is related to study intervention
- Assess study and subject safety to determine if stopping rules should be invoked
- Create the Safety Officer record in a blinded report format and communicate to Sponsor and with overall impression and recommended plan of action
- Responsible for determining the need to "unblind" the site investigator

Research Pharmacist

- Upon request, if necessary, unblind subject assignment and communicate to Medical Safety Monitor
- Suspend dispensing of study drug until SAE reporting is complete

Sponsor

- Receive and review Medical Safety Officer report with Pharmacist and Study Statistician
- Determine and implement stopping rules by communicating to site investigators, if required
- Ensure that IRB, FDA, and funding sponsors are notified as appropriate to local or agency policy
- Provide a copy of Medical Safety Officer report/record to appropriate personnel to file in eRegulatory Binder

Clinical Study Coordinator

• Ensure appropriate medical care and follow up is scheduled and implemented until SAE resolved

8.6. Stopping Rules

In the unlikely event that a study-related death or SAE occurs, the decision to stop the trial, either temporarily or permanently, will be the responsibility of the Medical Safety Officer in collaboration with the IND Sponsor.

Clinical excursions that a subject may experience that may warrant stopping study participation or drug administration either temporarily or permanently include but are not limited to:

- Clinical criteria:
 - Fever with a temperature > 101°F or other clinical indication of active illness
 - Blood pressure >170/95 or <90/50
 - Allergic reaction to drug
 - Serious nosebleeds or other localized side effects of drug administration
 - Hyponatremia (serum sodium < 135 mmol/L) and/or low serum osmolality (serum osmolality < 275 mOsm/kg).
 - Obtain serum sodium levels and osmolality at any time hyponatremia is suspected based on symptoms lethargy, muscle spasms, seizures, confusion/delirium, nausea and vomiting or physical examination
 - Any patient withdrawn from the study or has low sodium levels at the final visit will be evaluated until full normalization of the electrolyte abnormality occurs, and clinical and laboratory evaluations will be made available to medical safety monitor for review.
 - Other Serious Adverse Event adjudicated by medical safety monitor and invoking stopping rules

9. Data Handling and Record Keeping

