3.4. Potential Risks to Subject Safety

Drug Administration.

Rare: (observed in <1% of subjects)

- Nausea
- Allergic dermatitis
- Occasional abnormal uterine contractions (unlikely in post-menopausal subjects)
- Hyponatremia and or fluid imbalance

Mild: (observed in 10-20% of subjects)

- Light-headedness
- Vertigo
- Drowsiness
- Sleepiness
- Dry mouth
- Nasal irritation
- Runny nose
- Abdominal pain
- Anxiety
- Euphoria
- Increased energy
- Relaxation
- Calm sensation
- Headache

Blood withdrawal.

All studies involve the withdrawal of blood. Any subject who has donated blood in the previous two months will not be studied. The subjects will be instructed not to donate blood for two months after the study. Any subject with a hematocrit of < 34% will not be studied. Blood will be collected for safety and for research purposes at screening and study visits. Upon subject-reported history of any condition (known or suspected) that would be exclusionary, investigator may choose to order appropriate additional clinical labs to ensure eligibility.

IV lines.

Catheters will be placed in an antecubital vein or a hand vein for the OGTT. Local hematomas occur in about 1% of catheterizations. Infection is possible (<1%), but we have not experienced this complication.

Muscle biopsy.

At the time of biopsy, subjects may feel pain, discomfort, or pressure (variably described by different subjects) for about 5-10 seconds. Pain or discomfort ceases as soon as the cannula is withdrawn. Local hematomas occur in <2% of subjects. One patient experienced a moderately painful hematoma that resolved within 2 weeks (0.1%). About 1 in 50 subjects report non-clinically evident numbress or altered sensation at the biopsy site, which is transient.

There is the possibility that a future biopsy may not be done at the discretion of the PI in case the subject did not tolerate well a prior biopsy.

Radiation exposure.

Subjects will be exposed to a small amount of radioactivity during DEXA.

4. Subject Selection and Withdrawal

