6.6. Visit 6; Post treatment measurements (6-7.5 weeks on treatment)

Subjects present in fasting state to the site CRC to assess:

- Vital signs, weight, BMI, waist circumference
- Laboratory: CBC, chemistry with liver function, lipid panel, urine and serum osmolality, hemoglobin A1c, coagulation tests (PT/INR, PTT)
- Functional testing: Gait speed, grip strength, modified SPPB, TUG
- Food recall: same as Visit 1

- 2-hour OGTT
- Drug compliance and tolerability, AE review

6.7. Visit 7: Optional MRI (if done at V2) – (7-7.5 weeks on treatment)

MRI (optional): Image of the abdomen and dominant lower extremity will be done if completed at Visit 2. If participant has a pacemaker or any other reason that would preclude obtaining an MRI, this procedure can be omitted at the discretion of the PI.

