6.8. Visit 8: Post treatment measurements (7.5-8 weeks of treatment)

Subjects present in fasting state to the site CRC to assess:

- Vitals signs, weight, BMI, waist circumference
- MOCA, CES-D
- DEXA body composition, Bioimpedance (UTMB Galveston only) and Calorimetry
- Muscle biopsy (satellite cell, fiber type, fat infiltration, inflammation, gene expression)
- Blood draw: Systemic inflammation
- Drug tolerability, compliance, and AE review

See Summary of Visits Table on next page.

Summary of Visits Table

	Visit 1	Visit 2	Visit 3	Visit 4	Visit 5	Visit 6	Visit 7	Visit 8
			240		4 weeks	6-7.5	MRI	7.5-8
	Screen	MDI	V2	1 week on	on	weeks on	7-7.5	weeks on
	(fasting)	+ 7d	(fasting)	(fasting)	(fasting)	(fasting)	treatment	(fasting)
Medical history and	(raoting)		(idotilig)	(luoting)	(luoting)	(luoting)		(luoting)
physical examination.	Х							
ECG								
Vital signs, Weight, BMI	Х		Х	Х	Х	Х		Х
Waist circumference	Х			Х	Х	Х		Х
Mini-Cog	Х							
Montreal Cognitive	v				V			V
Assessment (MOCA)	~				~			~
Geriatric depression scale	V							
(GDS)	X							
Centers for Epidemiologic								
Studies Depression Scale	Х				X			Х
(CES-D)								
Gait speed, 15-foot course	Х					Х		
Electrocardiogram	Х							
**CBC. HobA1c. and								
Coagulation testing	Х					Х		
(PT/INR, PTT)								
**Chemistry with liver								
function, serum osmolality								
(other safety labs if	Х			Х	X	X		
clinically indicated by								
history)								
**Lipid Panel	Х					X		
Urinalysis	Х							
Urine osmolality	Х			Х	Х	Х		
OGTT, 2-hour	Х					Х		
Body composition (DEXA)			Х					Х
Bioimpedance (UTMB								×
only)			Х					^
Calorimetry			Х					Х
Randomization*			Х					
Body composition (MRI)		v					v	
- optional		^					^	
Functional tests: mSPPB,	v					v		
TUG, grip strength	^					^		
24-hour food recall, 3-day	v			v	×	×		
food diary, appetite	^			^	^	^		
Muscle biopsy			Х					X
Systemic inflammation			Х					Х
			AE					
			review	X	X	X		X
compliance, AE review			only					

* After Visit 4, participants may receive periodic phone calls by study staff between study visits to assess any symptoms and encourage adherence to study drug.

** Any marginally abnormal lab findings may be repeated if clinically indicated to ensure initial or continued eligibility.

7. Statistical Plan

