ATTACHMENT B. EVENT SCHEDULE

	Visit 1	Visit 2	Visit 3	Visit 4*	Visit 5	Visit 6	Visit 7	Visit 8
	Screen Day 0	MRI +7 days	V2 +7-14 days	1 week on Rx	4 weeks on Rx	6-7.5 weeks on Rx	7-7.5 weeks on Rx	7.5-8 weeks on treatment
Medical history and physical examination, ECG	х							
Vital signs, Weight, BMI,	Х		x	Х	X	X		x
Waist circumference	х			Х	х	x		x
Mini-mental status exam (Mini- Cog)	х							
Montreal Cognitive Assessment (MoCA)	х				x			х
Geriatric depression scale (GDS)	х							
Centers for Epidemiologic Studies Depression Scale	Х				х			Х
Gait speed, 15-foot course	Х					Х		
**Hematology (CBC, HgbA1c) and Coagulation testing (PT/INR, PTT)	х					х		
**Chemistry with liver function and serum osmolality	Х			Х	х	х		
**Lipid Panel	Х					Х		
**Urinalysis	Х							
**Urine osmolality	Х			Х	Х	Х		
Electrocardiogram	Х							
OGTT, 2 hour	Х					Х		
Body composition (DEXA)			X					Х
Bioimpedance (UTMB only)			X					Х
Calorimetry			X					Х
Randomization			X					
Body composition (MRI)		Х	Х				Х	
Functional tests: mSPPB, TUG, grip strength	х					х		
24-hour food recall, 3-day food diary, appetite	х			Х	х	х		
Muscle biopsy: satellite cell, fiber type, fat infiltration, inflammation, gene expression			x					Х
Systemic inflammation			Х					Х
Drug tolerability/ compliance, adverse event monitoring			AE review only	X	X	X		X

* After Visit 4, participants may receive periodic phone calls by study staff between study visits to assess any symptoms and encourage adherence to study drug.

** Any marginally abnormal lab findings may be repeated if clinically indicated to ensure initial or continued eligibility.

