12-20-16	1.2.3	ATTACHMENT E. Summary of Protocol Changes Table		Updated all changes to date by version in the Summary table.
		8.4 Medical Monitor	8.4, Page 16	Added "Contact Information: (see next page)" before listing his address, etc. on page 17
		ATTACHMENT B. Placeholder for Event Schedule	ATTACHMENT B., Event Schedule	Inserted Event Schedule from Page 12, Table 3, Study Visits and Procedures; corrected event schedule in 2 places to be consistent with ICF
03-17-17	1.2.4	Table of Contents	Update Visit Numbers	Renumbered Visit 3a-c, 4, 5a-c to
		3.1	Definition of Sarcopenic Obesity	Updated definition of Sarcopenic Obesity to reflect modified consensus. Muscle mass will be measured as an outcome
		6.3-6.5.3	Update Visit Numbers	Renumbered Visit 3a-c, 4, 5a-c to
		Table 3	Study Visits and	Renue Pered Visit 3a-c, 4, 5a-c to
		Table 12.3	Procedures Subject Stipend	Renumbered Visit 3a-c, 4, 5a-c to
		ATTACHMENT B	ATTACHMENT B	Renumbered Visit 3a-c, 4, 5a-c to visits 3-9
05-16-17	2.0	4.2 Exclusion Criteria 4.3 6.1c	GDS > 5	GDS > 7
		4.3	Screening tests	Remove ECG
		6.1	Visits 1 and 2	Combined to Visit 1, remove ECG, deleted unnecessary language
		6.1-6.8	Update Visit Numbers	Renumbered Visit 1-8
		Table 3	Study Visits and	Renumbered Visit 1-8, removed ECG,
		Table 12.3	Subject Stipend	Renumbered Visit 1-8
		ATTACHMENT B	ATTACHMENT B	Same as Table 3,
		Summary of Protocol Changes Table.		Updated to V2.0 all changes to protocol shown above

0008_Protocol v2.5, 08-03-18, AMD.docx

OXY-SAR-001 Version: 2.5

06-20-17	2.1	6.1	Visit 1	Added ECG back in
		6.2 and 6.3	Visits 2 and 3	Swapped visits 2 and 3 to have optional MRI occur before randomization. Provided PI discretion to forego optional MRI if necessary
		6.3	Visit 3	Baseline visit added to establish IV access for biopsy and UT Houston no calorimetry due to no equipment.
		6.7 and 6.8	Visits 7 and 8	Swapped visits 7 and 8 to have optional MRI occur before completion of study drug and final visit
		Visit Table	Visit Table	Swapped visit procedures to be consistent with narrative protocol
		Summary of Protocol Changes Table		Updated to V2.1 all changes to protocol shown for 06-20-17 version
10-03-17	2.2	Title Page, headers and footers	Version number and IND series #	Updating version numbering in header and footer to 2.2; IND# 0003 = v2.0 protocol, 0004 = v2.1 protocol, 0005 = v2.2 this version to be consistent with recent IND reporting to FDA

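### Section 8.6 acts on low sodium at the final visit, but no sodium or osmolality is scheduled at Visit 8, so silent hyponatremia arising after Visit 6 would go undetected

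*Combined protocol and SAP*

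**What the plan says.** Section 3.4 lists "Hyponatremia and or fluid imbalance" among the rare drug risks, meaning under 1% of subjects. Section 8.6 makes a serum sodium below 135 mmol/L, or a serum osmolality below 275 mOsm/kg, a possible reason to stop dosing or participation. It then gives two further instructions:

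- For-cause testing: "Obtain serum sodium levels and osmolality at any time hyponatremia is suspected", with suspicion resting on symptoms or the physical examination.
- Follow-up: "Any patient withdrawn from the study or has low sodium levels at the final visit will be evaluated until full normalization", with the results made available to the medical safety monitor.

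The scheduled measurements are as follows:

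- Section 6.6 (Visit 6, week 6 to 7.5) includes "CBC, chemistry with liver function, lipid panel, urine and serum osmolality".
- Section 6.8 (Visit 8, week 7.5 to 8) has one blood item: "Blood draw: Systemic inflammation".
- In Attachment B, the row "Chemistry with liver function and serum osmolality" is marked at Visits 1, 4, 5 and 6. The corresponding row of the Summary of Visits Table in section 6 is marked at the same four visits.

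**The concern.** The second limb of the follow-up rule depends on a sodium value at the final visit, and for completers the schedule does not produce one. A site that follows the visit tables exactly has nothing to which it can apply that limb, unless symptoms or examination findings have already prompted a test.

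A completer whose sodium falls late in treatment without recognised symptoms or signs would leave the study without the evaluation to normalization that section 8.6 intends. The safety record would also hold no sodium for the last part of dosing. The matter concerns participant safety and internal consistency, and does not touch the efficacy analysis.

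**Working it through.** **Step 1: which visit is final.** Visit 8 is the last column of both visit tables. The v2.1 entry in Attachment E, which matches the current visit order, reads "Swapped visits 7 and 8 to have optional MRI occur before completion of study drug and final visit". For a completer the final visit is therefore Visit 8.

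**Step 2: what is measured there.** Three places in the current text can be compared.

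| Place | Chemistry and serum osmolality |
|---|---|
| Sections 6.1, 6.4, 6.5, 6.6 (Visits 1, 4, 5, 6) | Listed |
| Section 6.8 (Visit 8) | Not listed; inflammation sample only |
| Summary of Visits Table | Visits 1, 4, 5, 6 |
| Attachment B | Visits 1, 4, 5, 6 |

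The visit narratives and the two tables agree, so the blank at Visit 8 is not an artefact of how the tables were extracted.

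**Step 3: dosing after the last scheduled sodium.** Inputs are 56 days at 4 doses a day (section 5.2), Visit 6 at week 6 to 7.5 (section 6.6) and Visit 8 at week 7.5 to 8 (section 6.8).

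- Total doses: 56 × 4 = 224.
- Visit 6 at its earliest, day 42: 56 − 42 = 14 days; 14 × 4 = 56 doses; 56/224 = 25%.
- Visit 6 at its latest, day 52.5: 56 − 52.5 = 3.5 days; 3.5 × 4 = 14 doses; 14/224 = 6.25%.
- With a panel at Visit 8 (day 52.5 to 56): 0 to 3.5 days, 0 to 14 doses, at most 6.25%.

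Section 8.1 extends adverse event reporting to 7 days after the last dose, but attaches no laboratory test to that period.

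**Step 4: how many cases.** Assume the 1% ceiling of the rare category in section 3.4 and the 18 oxytocin completers in section 7.1.

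- Whole eight weeks: 18 × 0.01 = 0.18 expected cases; chance of at least one = 1 − 0.99^18 = 0.165.
- Within the gap, if risk is constant over dosing: 0.18 × 0.0625 = 0.011 to 0.18 × 0.25 = 0.045 expected cases; chance of at least one = 1 − 0.99^(18 × 0.0625) = 1.1% to 1 − 0.99^(18 × 0.25) = 4.4%.

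These gap figures include symptomatic cases, which for-cause testing should find, so the number of silent cases is lower still.

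**The case against.** The strongest reply is that the clause sets a duty to follow up a low value and does not itself order a test. Where section 8.6 wants a test, it asks for one in the preceding instruction. On that reading the clause still applies to a low Visit 6 value that has not resolved, to a for-cause result, and to withdrawn subjects, whose final visit under section 4.4.1 includes safety labs. This is correct as far as it goes, and it confines the gap to completers with silent onset after Visit 6. It does not close the gap. The withdrawal visit in fact shows that the protocol treats safety labs as part of leaving the study, yet schedules them only for those who leave early.

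A second reply is that Visits 6 and 8 carry the same post-treatment heading and form one closing assessment, with its safety panel deliberately placed at Visit 6. Nothing in the text calls Visit 6 final, however, and both the visit order and the v2.1 log entry point to Visit 8. If Visit 6 was meant, section 8.6 needs rewording, so an edit is due either way.

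A third reply is that the risk is small and already guarded: abnormal sodium is excluded at entry, the dose is constant, sodium is checked at weeks 1, 4 and 6 to 7.5, and Visit 8 has a tolerability and adverse event review. This stands as a limit on severity. It is also true that the visit windows allow Visits 6 and 8 to fall together at week 7.5, and that a Visit 8 panel does little for the stopping rule because at most 3.5 days of dosing remain. Its value lies in follow-up after the study.

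The footnote allowing marginally abnormal labs to be repeated is discretionary and cannot reveal onset after a normal Visit 6 result.

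**Conclusion.** The concern holds. Section 8.6 sets a follow-up duty that the visit schedule cannot trigger for a completer whose hyponatremia begins after Visit 6 without raising clinical suspicion. Dosing beyond the last scheduled sodium runs from 3.5 to 14 days, depending on where Visit 6 falls in its window; the 14-day figure needs the earliest permitted date.

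Expected cases are well below one under any figure consistent with the protocol's rare category, and no endpoint or analysis changes. The case for acting rests on a stated safety duty lacking its scheduled measurement and on a cheap remedy, rather than on event counts. It should be fixed, but it is a moderate inconsistency.

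The conclusion assumes that the final visit for completers is Visit 8. Section 8.4 (medical monitoring) was not available to this review; the visit schedule itself sits in section 6 and Attachment B, both of which were.

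**What to change.** Add chemistry, including serum sodium, and serum osmolality to the fasting blood draw at Visit 8. This takes one line in section 6.8, plus a mark at Visit 8 in the chemistry and serum osmolality row of both the Summary of Visits Table and Attachment B. The final-visit clause in section 8.6 would then rest on a scheduled measurement for every completer.

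The cost is one panel per completer: 36 planned, and at most 3 × 15 = 45. Blood is already drawn at that visit, so no extra visit or needle stick is needed. The change is a protocol amendment and must go to the IRB under section 11; it could be bundled with the next one.

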9.1. Confidentiality

Information learned about all subjects will be kept confidential. All data and protected health information (PHI) in paper form will be kept confidential by assigned anonymous identifier and kept secured (password protected and/or double locked). Subjects will not be identified in any way in any publication.

9.2. Source Documents

Source data are contained in source documents found in paper subject files at the research site and in site electronic medical records. If source data are handwritten, print all entries legibly in black ink. Erasures and white-out material are prohibited. If any entry error has been made on paper, to correct such an error, draw a single straight line through the incorrect entry and enter the correct data above it. All such changes must be initialed and dated. For clarification of illegible or uncertain entries, print the clarification above the item, then initial and date it.

